The sampling of whole blood for pharmacogenomic and genotyping analysis is mandatory; eligible subjects sign the ICF, which outlines the retention of pharmacogenomic and genotyping analysis in order to participate in this study. DNA samples will be collected and may be used to evaluate drug metabolic enzyme and transporter polymorphisms that may contribute to the variability in the PK of CVN766. Also, since pharmacogenomics is an evolving science, many genes and their functions are not yet fully understood. Future data may suggest a role of some of these genes in drug response, which may lead to additional hypothesis-generating exploratory research and diagnostic development on stored samples.

- Endpoints:

The primary endpoints of this study will be the following: percentage of subjects who experience at least one treatment-emergent adverse event (TEAE); percentage of subjects with abnormal and CS safety laboratory, vital signs, or ECG test results at least once post-dose.

The secondary endpoints will be the following plasma PK parameters of CVN766: C_{max} , AUC_{24} , AUC_{∞} , $t_{1/2z}$, AUC from time 0 to end of the dosing interval, accumulation ratio, time to steady-state, steady-state C_{max} , and steady-state C_{min} .

The additional endpoints may include the following plasma PK parameters of CVN766: t_{max} , CL/F, V_z/F , CL/F_{ss}, V_z/F_{ss} , and plasma: CSF ratio.

Exploratory endpoints may include characterization of metabolic enzyme and transporter polymorphisms and/or

Statistical Considerations:

Safety:

AEs will be presented in listings, and TEAEs will be summarized. Individual results of laboratory tests (hematology, chemistry, and urinalysis) will be recorded at baseline and post-dose, and changes from baseline will be summarized using shift tables. Individual vital signs will be recorded, and observed values and changes from baseline will be summarized. Individual results of quantitative ECG parameters from the 12-lead safety ECGs will be listed, and observed values and changes from baseline will be summarized. All summaries will be performed by placebo, each CVN766 dose level (fasted and fed separately), and CVN766 single-dose overall, and separately CVN766 multiple-dose cohorts overall. Placebo data will be pooled across single-dose cohorts and separately pooled across multiple-dose cohorts. Physical exam findings will be presented in data listings.

PK Measures:

Concentrations of CVN766 in plasma and CSF will be summarized by dose over each scheduled sampling time using descriptive statistics. Individual plasma and CSF concentration data versus time will be presented in a data listing. Individual and mean plasma and CSF concentration data will be presented graphically.

PK parameters of CVN766 will be summarized by dose using descriptive statistics. Dose proportionality will be assessed graphically and using a power model.

The concentrations of CVN766 in plasma and CSF will be compared.

Sample Size Justification:

The sample size chosen is considered sufficient for evaluating the safety, tolerability, and PK of each cohort. The sample size was not based on statistical power considerations.

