5.2 Endpoints

5.2.1 Primary Endpoints

- Percentage of subjects who experience at least one treatment-emergent adverse event (TEAE)
- Percentage of subjects with abnormal and clinically significant (CS) safety laboratory test results at least once post-dose
- Percentage of subjects with abnormal and CS electrocardiogram (ECG) test results at least once post-dose
- Percentage of subjects with abnormal and CS vital sign measurements at least once post-dose

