6.1.1 Part 1: Single-Dose Regimen and Fasted-Fed Crossover

Approximately 40 subjects will be enrolled in 1 of the 5 single-dose cohorts (designated as S1 through S5, respectively) in an ascending fashion. An optional Cohort 3a may be added in parallel to SC3 for additional safety and tolerability evaluation. Cohort S3a dose level will be consistent with Cohort S3 (45 mg planned) in a fasted condition only and without lumbar puncture, aligned with the Schedule of Procedures (**Appendix A**) and other SAD cohorts. Dose escalation will only occur after a fully blinded review of all available safety, tolerability, clinical laboratory results (minimally including samples collected from subjects through 72-hours post-dose), and available PK data, including at least a 72-hour follow-up from a minimum of 5 subjects of the most recent cohort.

The planned dose levels are provided in **Table 5**. Each cohort will consist of 8 subjects randomized to CVN766 or placebo, whereby 6 subjects will receive a single dose of CVN766 and 2 subjects will receive a matching placebo under overnight fasted conditions.

Sentinel dosing (1 subject to receive CVN766 and 1 subject to receive placebo) will be used in each cohort to ensure adequate safety and tolerability evaluation prior to administering CVN766 to the remainder of the subjects within the cohort. After a blinded review of 24-hour post-dose safety and tolerability data, the remaining 6 subjects of each cohort may be dosed, provided that the adverse event (AE) profile of CVN766 in the first 2 subjects is considered acceptable.

Subjects for all cohorts (including optional Cohort S3a) will be admitted to the study unit 1 day prior to dosing and remain in the unit for safety and PK assessments at least 72 hours after dosing. On Day 1, subjects will undergo safety monitoring (including labs, physical exam, neurological exam, cardia telemetry at 12-hours pre-dose), and PK sampling from blood plasma through 72 hours post-dose. In addition, for Cohort S3 (fasted) only, from CSF via lumbar puncture at 3 hours post-dose. For subjects participating in the SAD cohorts, the total confinement period will be 4 nights unless extended for management of AEs at the discretion of the Investigator. Follow-up assessments will occur on approximately Days 8 and 14.

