6.1.2 Part 2: Multiple-Dose Regimen

For the multiple-dose regimen, approximately 24 subjects will be enrolled in 1 of the 3 multiple-dose cohorts (designated as M1 through M3, respectively) in an ascending fashion. Dosing will be administered in the fasting state; this can be changed by the SRG if exposure is found to be higher in the fed state. The dose levels planned to be studied in the multiple-dose regimen (M1 through M3) are provided in **Table 5**. Each multiple-dose cohort will consist of 8 subjects randomized to CVN766 or placebo, whereby 6 subjects will receive a daily dose of CVN766, and 2 subjects will receive matching placebo for 7 days. However, the duration may be increased to ≤14 days at the discretion of the safety review group (SRG) if preliminary PK data suggest steady-state will not be achieved within 6 days of daily dosing. Unlike the single-dose regimen, sentinel dosing within cohorts is not required in the multiple-dose regimen.

Subjects for all multiple-dose cohorts will be admitted to the study unit 1 day prior to dosing and remain in the unit for the duration of the dosing period and for at least 48 hours after the last dose for safety and PK assessments before discharge. On treatment Days 1 and 7, subjects will undergo safety monitoring and PK sampling from blood plasma through 48 hours post-dose and, in Cohort M1 only, from urine through 24 hours post-dose. In Cohorts M1 and M2, on treatment Day 7 (or last day of dosing, if extended beyond Day 7), subjects will undergo additional PK sampling from CSF via lumbar puncture at 3 hours post-dose. If the SRG determines additional PK sampling from CSF via lumbar puncture is not necessary for Cohort M2, the lumbar puncture may be omitted. Likewise, if needed to resolve questions arising from prior Cohorts’ data, subjects in Cohort M3 also may, at SRG discretion, undergo PK sampling from CSF via lumbar puncture, the choice of day (e.g., Day 1 or Day 7) and sampling time to be decided by SRG. Subjects in MAD cohorts may be asked to return to the clinic for an additional plasma PK sample 3 days after the last dose (e.g., Day 10) depending on emerging PK data, i.e., $t_{1/2}$. The total confinement period will be 9 nights unless extended for additional dosing days or management of AEs. Follow-up assessments will occur approximately 7 and 14 days after the final dose. A summary of multiple-dose study visits is included in **Appendix A**.

Table 2 Multiple Dose Visit Schedule

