9.7.3 Additional Points to Consider for PTEs and AEs

An untoward finding generally may:

- Indicate a new diagnosis or unexpected worsening of a pre-existing condition. (Intermittent events for pre-existing conditions underlying disease should not be considered PTEs or AEs)
- Necessitate therapeutic intervention
- Require an invasive diagnostic procedure
- Require discontinuation or a change in dose of study medication or a concomitant medication
- Be considered unfavorable by the Investigator for any reason

- PTEs/AEs caused by a study procedure (e.g., a bruise after blood draw) should be recorded as a PTE/AE

Diagnoses vs. signs and symptoms:

- Each event should be recorded to represent a single diagnosis. Accompanying signs (including abnormal laboratory values or ECG findings) or symptoms should NOT be recorded as additional AEs. If a diagnosis is unknown, sign(s) or symptom(s) should be recorded appropriately as a PTE(s) or as an AE(s).

Laboratory values and ECG findings:

- Changes in laboratory values or ECG parameters are only considered to be PTEs or AEs if they are judged to be CS (i.e., if some action or intervention is required or if the Investigator judges the change to be beyond the range of normal physiologic fluctuation). A laboratory re-test and/or continued monitoring of an abnormal value are not considered an intervention. In addition, repeated or additional noninvasive testing for verification, evaluation, or monitoring of an abnormality is not considered an intervention
- If abnormal laboratory values or ECG findings are the results of pathology for which there is an overall diagnosis (e.g., increased creatinine in renal failure), the diagnosis only should be reported appropriately as a PTE or as an AE

Pre-existing conditions:

- Pre-existing conditions (present at the time of signing of the ICF) are considered concurrent medical conditions and should NOT be recorded as PTEs or AEs. Baseline evaluations (e.g., laboratory tests, ECG, X-rays, etc.) should NOT be recorded as PTEs unless related to study procedures.
- If a subject has a pre-existing episodic condition (e.g., asthma, epilepsy), any occurrence of an episode should only be captured as a PTE/AE if the episodes become more frequent, serious, or severe in nature; that is, Investigators should ensure that the AE term recorded captures the change in the condition from Baseline (e.g., “worsening of...”)

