9.7.7 Relationship to Study Procedures

Relationship (causality) to study procedures should be determined for all PTEs and AEs.

The relationship should be assessed as Related if the Investigator considers that there is a reasonable possibility that an event is due to a study procedure. Otherwise, the relationship should be assessed as Not Related.

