12.1.4 Safety Analysis

12.1.4.1 AEs

All AEs will be coded by system organ class (SOC) and preferred term (PT) using MedDRA. Treatment-emergent AEs with onset occurring within 30 days (onset date – last date of dose +1 \leq 30) after study drug administration will be listed and included in the summary tables. Treatment-emergent AEs will be summarized by pooled placebo, each CVN766 dose level and CVN766 overall by SOC and PT. The following summary tables will be included in the report: summary of TEAEs and drug-related AEs, relationship of AEs to study drug (related vs. not-related), severity of AEs, and related AEs. AEs leading to study drug discontinuation and SAEs will be listed. Data listings will be provided for all AEs, including PTE, TEAEs, AEs leading to study drug discontinuation, and SAEs. All AEs will be listed.

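### Pooling placebo over cohorts with and without lumbar puncture puts procedure-caused AEs unevenly into the by-dose TEAE percentages; add a TEAE summary that leaves them out

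*Protocol*

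**What the plan says.** References are to the later of the two protocol versions in the file, the one that adds optional cohort S3a. Both versions carry the same pooling sentence.

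- **Comparator.** Study Summary, Statistical Considerations: "Placebo data will be pooled across single-dose cohorts and separately pooled across multiple-dose cohorts". The display groups are given just before: "All summaries will be performed by placebo, each CVN766 dose level (fasted and fed separately), and CVN766 single-dose overall", with a separate overall group for multiple dosing. Section 12.1.4.1 also summarises TEAEs by pooled placebo, each dose level and CVN766 overall.
- **Who is punctured.** Section 6.1.1: "for Cohort S3 (fasted) only, from CSF via lumbar puncture at 3 hours post-dose". Section 6.1.2, for M1 and M2 on the last dosing day: "subjects will undergo additional PK sampling from CSF via lumbar puncture at 3 hours post-dose". The Safety Review Group (SRG) may drop the M2 puncture or add one in M3. S3a (45 mg, fasted) has none. Section 9.1.1.1 makes CSF sampling mandatory in the cohorts concerned, so placebo subjects there are punctured too.
- **What counts.** Section 9.7.3: "PTEs/AEs caused by a study procedure (e.g., a bruise after blood draw) should be recorded as a PTE/AE". Section 5.2.1 makes the percentage of subjects with at least one TEAE the first primary endpoint.
- **What is collected and tabulated.** Section 9.7.7: "Relationship (causality) to study procedures should be determined for all PTEs and AEs". Section 9.8.1.2 (item 6) adds details of the suspected procedure. The tables named in Section 12.1.4.1 cover "relationship of AEs to study drug (related vs. not-related), severity of AEs, and related AEs". None of them uses relationship to procedure.

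**The concern.** Each punctured cohort is randomised 6:2, so it has its own punctured placebo subjects. Pooling gives up that match. A treated group that is always punctured is then set beside a placebo column that mostly is not, or the reverse, and the dose contrast carries part of the effect of an invasive procedure.

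The relationship-to-drug tables do not clearly remove this. Section 9.7.6 counts an event as related when drug involvement can be argued even though other factors may be responsible, so a headache after a puncture at 3 hours post-dose could be coded as related. Section 4.1 lists mild headache among the most common AEs of other selective Ox1R antagonists, so procedure and drug signals can look alike.

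At stake is the reading of the side-by-side primary percentages. They could suggest a tolerability signal at 45 mg and flatter 250 mg multiple dosing. The Study Summary's primary objective includes determining the recommended phase 2 dose.

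**Working it through.** **Cohort sizes.** Section 8.1.3, Table 5, gives 6 active and 2 placebo per cohort. The stated total reproduces: (5 + 3) × 8 = 64. With S3a it would be 72. Pooled placebo is 5 × 2 = 10 for single dose and 3 × 2 = 6 for multiple dose.

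**Step 1: share punctured, default plan (no S3a, puncture in M1 and M2, none in M3).**

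| CVN766 group | Active | Pooled placebo | Difference d |
|---|---|---|---|
| 45 mg single, fasted (S3) | 6/6 | 2/10 | +80 points |
| Other single doses; 45 mg fed | 0/6 | 2/10 | -20 points |
| M1, M2 (each) | 6/6 | 4/6 | +33 points |
| M3 | 0/6 | 4/6 | -67 points |

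**Step 2: variants the protocol allows.**

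- M2 puncture omitted: M1 is 6/6 vs 2/6 (+67) and M3 is 0/6 vs 2/6 (-33).
- M3 puncture added, M2 kept: M3 is 6/6 vs 6/6 (0).
- M3 puncture added, M2 omitted: M3 is 6/6 vs 4/6 (+33).
- S3a enrolled and merged with S3 as 45 mg fasted: 6/12 vs 2/12 (+33).

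**Step 3: effect on the endpoint.** Let q be the chance that a puncture causes an AE and p0 the background risk of at least one TEAE, with the two independent and no drug effect. A punctured subject has at least one TEAE with probability p0 + (1 - p0)q. The factor (1 - p0) is needed because a subject who would have had a TEAE anyway adds nothing. The spurious difference is

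d × q × (1 - p0).

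The protocol gives neither q nor p0. I take q from 10% to 40% and p0 from 20% to 50%. The smallest product q(1 - p0) is 0.10 × 0.50 = 0.05 and the largest is 0.40 × 0.80 = 0.32.

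- 45 mg fasted: 0.80 × 0.05 = +4.0 points to 0.80 × 0.32 = +25.6 points.
- M1, M2: 0.333 × 0.05 = +1.7 to 0.333 × 0.32 = +10.7 points.
- M3: -0.667 × 0.05 = -3.3 to -0.667 × 0.32 = -21.3 points.
- 45 mg fed and the other single doses: -0.20 × 0.05 = -1.0 to -0.20 × 0.32 = -6.4 points.

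**Step 4: one worked case, q = p0 = 30%.** Here (1 - p0)q = 0.21.

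- 45 mg fasted: 30 + 21 = 51.0% against 30 + 0.2 × 21 = 34.2%, a difference of +16.8 points.
- M1: 51.0% against 30 + 0.667 × 21 = 44.0%, a difference of +7.0 points.
- M3: 30.0% against 44.0%, a difference of -14.0 points.

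**Step 5: would a matched placebo column be better?** For the same case, compare root-mean-square errors of the placebo estimate.

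- S3 fasted, target 51%. Matched (n = 2): √(0.51 × 0.49 / 2) = 0.35. Pooled: √[0.168² + (8 × 0.21 + 2 × 0.2499)/100] = 0.22.
- M3, target 30%. Matched (n = 2): √(0.21 / 2) = 0.32. Pooled: √[0.14² + (2 × 0.21 + 4 × 0.2499)/36] = 0.24.

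In this case the matched column removes the bias but is the noisier estimate.

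**The case against.** The strongest reply has four parts.

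1. *The analysis is descriptive.* No test is planned for TEAEs and the sample size is not based on power. That stands, and it limits the consequence to how the percentages read. With no test, however, those percentages are the primary result.
2. *Dose escalation does not use this table.* The SRG reviews blinded data cohort by cohort (Section 6.1.3). That also stands. A reader might infer that the pooling endangers escalation decisions; the protocol does not support that. Blinded review does not protect the final by-dose summary.
3. *The SAP may add tables.* Section 12.1 defers detail to a SAP that is not at hand, and Section 12.1.4.1 does not call its list exhaustive. So it cannot be said that no table will ever use relationship to procedure. The pooling rule itself, though, is fixed in the protocol. Tables by preferred term and full AE listings would let a careful reader find puncture events, but would not correct the headline percentage.
4. *Splitting placebo costs too much precision.* This stands. The matched groups are 2 subjects for S3 fasted, 4 for M1 and M2, and 2 for M3; with 2 subjects a rate can only be 0, 50 or 100%.

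A reader might also object to pooling fed with fasted placebo. That is secondary. It gives the two S3 placebo subjects a second observation period but does not drive the puncture imbalance, and nothing in the protocol supports extending a split to vital signs or ECG.

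**Conclusion.** The concern holds under the default plan. The puncture shares follow from the protocol's own schedule and allocation, and they fix the direction: up for 45 mg single-dose fasted, M1 and M2; down for M3; slightly down for 45 mg fed and the other single doses. The size rests on the assumed q and p0 and on no drug effect: +4.0 to +25.6 points for 45 mg fasted and -3.3 to -21.3 points for M3.

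Two stronger readings are tempting and do not hold. The first is that every 45 mg comparison is inflated and the top multiple dose always flattered. The fed group goes the other way, and merging S3a would cut the fasted gap from +80 to +33 points of puncture share. The M3 bias halves if the M2 puncture is dropped, vanishes if puncture is added in M3, and reverses to +33 points if both happen. The second is that the spurious difference equals the difference in puncture-caused events, 0.8q or 0.67q. That ignores background TEAEs and is too large for an endpoint that counts subjects with at least one.

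This is a distortion of descriptive percentages that is cheap to address. It is not an error in any test or power figure.

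**What to change.** Keep the pooled-placebo TEAE table. In Section 12.1.4.1 add one prespecified TEAE summary with the same columns, for any TEAE and by SOC and PT, excluding events judged related to lumbar puncture. Identify them from the relationship-to-procedure field and the procedure details already collected under Sections 9.7.7 and 9.8.1.2. Fix the rule before unblinding. Placebo counts by puncture status may be shown for description, but not as the sole comparator.

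The cost is one extra table and no new data. If attribution were perfect, the expected puncture bias would be zero in every column. In practice it rests on the investigator's blinded judgement: a puncture headache put down to the drug would stay in, and a drug headache put down to the puncture would drop out. That is why the two tables should be read together. No change to the puncture schedule is needed.

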3.0 STUDY REFERENCE INFORMATION

3.1 List of Abbreviations

λ_z	terminal elimination rate constant
AE	adverse event
█	█
ALT	alanine aminotransferase
AST	aspartate aminotransferase
AUC	area under the plasma concentration-time curve
AUC ₂₄	area under the plasma concentration-time curve from time 0 to 24 hours
AUC _∞	area under the plasma concentration-time curve from time 0 to infinity
AUC _t	area under the plasma concentration-time curve from time 0 to the last quantifiable concentration
AUC _t	area under the plasma concentration-time curve over the dosing interval (t)
BMI	body mass index
CL/F	apparent clearance after extravascular administration
CL/F _{ss}	apparent clearance after extravascular administration at steady state
█	█
C _{max}	maximum observed plasma concentration
C _{min}	minimum observed plasma concentration
CNS	central nervous system
CS	clinically significant
CSF	cerebrospinal fluid
ECG	electrocardiogram
eCRF	electronic case report form
FDA	Food and Drug Administration
█	█
FSH	follicle-stimulating hormone
FT4	free T4
GCP	Good Clinical Practice
GGT	γ-glutamyl transferase
HBsAg	hepatitis B surface antigen
hCG	human chorionic gonadotropin
HCV	hepatitis C virus
HED	human-equivalent dose
ICF	informed consent form
ICH	International Council on Harmonisation
IEC	independent ethics committee

INR	international normalized ratio
IRB	institutional review board
K ₂ EDTA	dipotassium ethylenediamine tetraacetic acid
LFT	liver function test
MAD	multiple-ascending dose
MedDRA	Medical Dictionary for Regulatory Activities
MRSD	maximum recommended starting dose
NCS	not clinically significant
NOAEL	no-observed-adverse-effect-level
Ox1R	orexin 1 receptor
Ox2R	orexin 2 receptor
PK	pharmacokinetic
PRL	prolactin
PT	preferred term
PTE	pretreatment event
QTcB	QT interval with Bazett's correction method
QTcF	QT interval with Fridericia's correction method
RNA	ribonucleic acid
RO	receptor occupancy
SAE	serious adverse event
SAD	single-ascending dose
SAP	statistical analysis plan
SOC	system organ class
SRG	Safety Review Group
SUSARs	suspected unexpected serious adverse reactions
t _{1/2z}	terminal elimination half-life
TEAE	treatment-emergent adverse event
t _{max}	time to reach C _{max}
ULN	upper limit of normal
V _z /F	apparent volume of distribution after extravascular administration
V _z /F _{ss}	apparent volume of distribution after extravascular administration at steady state
WHO	World Health Organization

4.0 INTRODUCTION

4.1 Background

The neuropeptide orexin, also known as hypocretin, is produced exclusively in the orexigenic neurons in the hypothalamus. There are two forms of orexin, Orexin-A, and orexin-B, alternatively spliced from the same gene, HCRT. There are two orexin receptors, orexin 1 receptor (Ox1R) and orexin 2 receptors (Ox2R), both of which are G-protein coupled receptors. Both orexin-A and orexin-B can bind to either receptor and in each case, agonist binding results in an increase in intracellular calcium levels. However, while orexin-A is equipotent at both receptors, orexin-B shows a 10-fold selectivity for Ox2R.

Ox1R is selectively expressed in key brain areas relating to psychiatric disorders. Ox1R-expressing neurons in the bed nucleus of the stria terminalis, amygdala, locus coeruleus, raphe nucleus, and the ventral tegmental area are important in regulating emotions of stress, anxiety, motivation, and reward. CVN766 is a potent and highly selective small-molecule Ox1R antagonist with no significant off-target activity. Nonclinical PK and toxicology studies with CVN766 and other Ox1R antagonists have established their pharmacological characteristics and probable safety profile.

Ox2R is expressed in some overlapping areas, including the raphe nucleus, and ventral tegmental area, but also in areas important to arousal and sleep regulation, including the tuberomammillary nucleus.

The widely used sleep aid suvorexant (Belsomra[®]), approved for use in Australia, is a dual Ox1R and Ox2R antagonist, but its sleep-inducing effects are generally attributed to its activity on Ox2R. A second dual Ox1R and Ox2R antagonist, lemborexant, appeared safe and effective in clinical studies, has been approved in many countries worldwide, and has been submitted for marketing authorization in Australia.

Clinical effects to be expected of a selective Ox1R antagonist remain uncertain. CVN766 has not yet been studied in humans. Other selective Ox1R antagonists have been reported in early-stage human clinical trials, notably JNJ-61393215 (ClinicalTrials.gov Identifier: NCT04080752; Salvadore *et al.*, 2020) and ACT-539313 (NCT01954589; Kaufmann *et al.*, 2020; Kaufmann *et al.*, 2021). Both drugs were well tolerated and deemed safe for investigational use, the most common AEs being somnolence and mild headache.

